## 9.5. Acceptability

Acceptability generally refers to *‘The overall ability and willingness of the patient to use and its caregiver to administer the medicine as intended’* (41). In this definition, the word “medicine” refers here to the therapeutic entity as it is to be delivered to the end user and includes: the type of dosage form, its formulation i.e., its composition and appearance, the dose of active substances, the dosing frequency, and the primary packaging. In this specific case, the product is a single scored dispersible tablet of DTG for suspension in water to be administered to HIV-exposed neonates.

The precise contribution of acceptability to adherence is difficult to establish (42, 43) but acceptability may have a direct impact on the efficacy and safety of a medication, while the level of adherence may impact efficacy and safety secondarily.

Our aim is to identify all obstacles that may prevent HIV-exposed neonates “from using and caregivers from administering the medicine as intended”. Assessment will take into account and document the relevant characteristics of the children and/or their caregivers:

- Age
- Inherent ability of the child to take the medicine; dependence on caregiver to prepare and administer it.

And measure key characteristics of the medicinal product:

- Palatability
- Swallowability (related to the volume of the intake and the texture of the suspension after reconstitution, depending on the vehicle) as well as the device used to administer the dose.
- The complexity for the caregiver to prepare the dose correctly prior to administration, if required (determination of the dose, weight band width and frequency of dose adjustment)
- Required dose (e.g., the dosing volume after product reconstitution).
- Need for a vehicle (e.g., water, formula milk, breastmilk)
- Dosing frequency and duration of treatment (once or twice daily)
- Selected administration devices (e.g., syringe, or cup) (44)
- Primary container closure system
- Actual mode of administration that reflects understanding of user instructions and feasibility of following them

In this study, acceptability will be recorded for all cohorts during each PK visit by focusing on several observation items:

- Attitude of the child when presented with the formulation: facial expression, crying or smiling, reaction to drug intake, fighting drug intake, incident e.g., spitting out the suspension, etc.
- Swallowability, i.e., ability to take the full dose, in one or two steps
- The way the caregiver prepares the dose (e.g., breaking the scored tablet, mixing with the appropriate volume of water, using an appropriate dosing device, calculating the right dose, etc)

In between visits, the experience of the caregiver preparing the medicine and administering it will be assessed as well as how the child reacted to medicine intake, ability to swallow the full dose, and incidents/accidents.

## 10. Safety Reporting

### 10.1. Adverse Event Definition

An adverse event (AE) is defined as *any* untoward medical occurrence (any unfavourable and unintended sign, symptom, or disease, including an abnormal laboratory finding) in temporal association with the use of the study drug, which may or may not be causally related to the study drug. Abnormal laboratory (haematology and biochemistry) results will be reported as AEs if the abnormality newly occurs or worsens after institution of the study treatment. Any untoward medical occurrence identified from birth to the time of study treatment will be considered a pre-existing condition.

### 10.2. Serious Adverse Event Definition

***An AE is defined as serious if it meets at least one of the following criteria below:***

- fatal
- life-threatening
- requires or prolongs hospitalization
- results in persistent or significant disability
- any important medical event

**Additional serious adverse events (SAEs) for this study protocol are:**

- any Grade 3 or higher adverse event on the DAIDS toxicity table
- for abnormal renal function and high bilirubin levels, any Grade 3 or higher adverse event as classified by the **protocol specific safety criteria** (refer to **Table 9**)

**10.3. Adverse Event Notification Procedure**

The investigator is required to report all directly observed AEs and all AEs reported by the parents using concise medical terminology. The adverse events reporting period for this trial begins with participant informed consent until the study ends. Each AE must be evaluated by a physician directly involved in the clinical evaluation of the research participants. The investigator must classify all AEs as serious or non-serious using the definitions above *and* determine relation to study drug. The AEs should be reported on study CRFs, regardless of their relationship to study drug. This classification, as well as the evaluation of severity and causal relationship, will determine the reporting procedure for the AE.

**Non-serious adverse events** are to be reported on the AE CRFs only and will be submitted to the Stellenbosch University Human Research Ethics Committee (SU-HREC). All events will be reviewed by the Serious Adverse Event Evaluation Group. On the CRF, a given AE will be recorded only one time per patient, and the severity recorded will be the maximum level reached. If several distinct episodes of the same condition occur, their number will be recorded in the CRF.

**All serious adverse events** will be reported in an *expedited manner*, irrespective of their relationship to study drug. All SAEs (as defined in Section 10.2) will be completed on a standard SAE report form and submitted to the SU-HREC **immediately, but no later than 3 reporting days** after the site becomes aware of an event that meets criteria for expedited reporting. The time frame for expedited reporting of individual SAEs begins when the clinical research site recognizes that an event fulfils the criteria for expedited reporting. Immediate clinical management of all adverse events will be the responsibility of the local study team. All SAEs will be followed and reported until resolution or stable state. On a monthly basis, all SAEs will also be reviewed by a Serious Adverse Event Evaluation Group (Section 14.2).

**10.4. Adverse Event Severity Grading**

AEs and toxicities will be graded for severity according to the DAIDS Table for Grading the Severity of Adult and Paediatric Adverse Events (Version 2.1, July 2017; available at: <https://rsc.niaid.nih.gov/sites/default/files/daidsgradingcorrectedv21.pdf>). It is to be noted there exists a distinction between severity (grade, reflecting degree of abnormality of the event) and seriousness (reflecting the immediate consequences) of adverse events.

In case of AEs not described in the DAIDS Table, the investigator will use the terminology “mild”, “moderate”, “severe” or “life-threatening” or “death” to describe the maximum severity of the adverse event.

These severity grades are defined as follows:

MILD	Does not interfere with patient's usual functions
MODERATE	Interferes to some extent with patient's usual functions
SEVERE	Interferes significantly with patient's usual functions
LIFE-THREATENING	The patient is at risk of death at the time of the AE: it does not refer to an AE that hypothetically might have caused death if more severe
DEATH	Death related to AE

**Protocol specific safety criteria (Table 9)** will be used to evaluate renal function and high bilirubin levels and replace the DAIDS toxicity table for these parameters.

**Table 9.** Protocol Specific Safety criteria

Parameters	Grade 1	Grade 2	Grade 3	Grade 4
Creatinine, High ( $\mu\text{mol/L}$ )	1.1 to 1.3 x ULN	> 1.3 to 1.8 x ULN	> 1.8 to < 3.5 x ULN	$\geq 3.5$ x ULN
Bilirubin, High	Mild jaundice, no treatment	Phototherapy	Exchange transfusion	Acute bilirubin encephalopathy

Creatinine will be graded according to the upper limits of 'normal' for a term neonate (**Table 9**), which will serve as a proxy for evaluating abnormal renal function. Study investigators will make use of protocol specific creatinine laboratory reference ranges (Appendix, **Table 18.1**) representing standardised accepted 'normal' creatinine levels for term neonates (45). At birth, creatinine values are elevated and reflect maternal renal function. Over the first 24 to 36 hours, a transient raise in creatinine levels occur, after which it falls quickly (day 5- 7 of life), and then creatinine levels stabilize at around 9 days (46). Given these renal physiological adaptations, a change from baseline creatinine and/ a change in creatinine clearance as per the DAIDS toxicity grading table will *not be used*, as these grading developed for children may be inaccurate in neonates.

A clinical grading system was developed for reporting hyperbilirubinemia making use of both clinical findings and intervention levels required to manage jaundice in the neonate (**Table 9**). Hyperbilirubinemia values will be captured and jaundiced will be managed according to the 2006 Western Cape Consensus Guidelines (Appendix, Section 18.2 (47)), as per standard of care. Neonates on phototherapy will be allowed to continue with study drug. Dolutegravir will be permanently discontinued in any neonate who requires an exchange transfusion.

### 10.5. Adverse Event Causality Assessment

For both non-serious and serious adverse events, the investigator is required to assess the possible relationship between the adverse event and the study drug, i.e., determine whether there exists a reasonable possibility that the study drug caused or contributed to the AE.

Relatedness of these events should be reported as follow:

- Related. There is a reasonable possibility that the adverse event may be related to the administration of study agent.
- Not related. There is no reasonable possibility that the adverse event may be related to the administration of study agent.

## 10.6. Hypersensitivity Reaction to Dolutegravir

Hypersensitivity reactions to DTG have been reported in less than 1% of participants in Phase 3 clinical trials and were characterized by rash, constitutional findings, and sometimes organ dysfunction, including liver injury. The DAIDS Toxicity Table will capture symptoms and signs of possible DTG hypersensitivity, and if suspected, will be managed as a SAE. Hypersensitivity to DTG is a multi-organ clinical syndrome usually characterized by fever, rash, general malaise, blisters or peeling of the skin, oral blisters or lesions, conjunctivitis, facial oedema, hepatitis, eosinophilia, angioedema, and difficulty in breathing. Clinical status, including liver aminotransferases, should be monitored and appropriate therapy initiated. Discontinue DTG as soon as a hypersensitivity reaction is suspected and if the diagnosis of DTG hypersensitivity is made DTG should never be re-started (17).

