## 10.8. Participant Study Drug Discontinuation Criteria

For all AEs/toxicity, the management and temporary/permanent discontinuation of the study drug should generally follow the criteria below, but clinicians should use their clinical judgment as to the best management for an individual participant.

- Grade 1 and Grade 2 AEs/toxicity:  
Continue the study drug. Manage using symptomatic measures and other concomitant medication, if appropriate.
- Grade 3 AEs/toxicity:  
Request laboratory results and repeat confirmatory laboratory results within 72 hours if relevant. Continue study drug pending receipt of the confirmatory laboratory tests/repeat observations, unless there is an immediate need to substitute ART. Continue to work-up to exclude other causes. Following confirmation of toxicity, and lack of other cause data (i.e., possibly, probably, or definitely related to the study drug) hold the treatment and follow abnormal laboratory values until they are Grade 2 or less.
- Grade 4 Potentially Life-Threatening or Fatal AEs/toxicity:  
Request laboratory results and repeat confirmatory laboratory results within 72 hours if relevant. Withhold the study drug at the discretion of the site investigator/ health care provider for clinical events, while awaiting a repeat assessment/ confirmation of an abnormal laboratory test. Continue to investigate to exclude other causes and make an assessment on relation to study drug or not. Following confirmation of toxicity and lack of other cause data: (i.e., possibly, probably, or definitely related to the study drug) the study drug should be discontinued immediately. Participants who permanently discontinue study treatment due to an adverse event related to the study treatment will continue to be followed in the study for safety monitoring at intervals to be determined by the investigator in consultation with the study team.

Study drug will be **permanently discontinued in participants** with the following condition:

- any grade 4 event on the DAIDS toxicity table
- a bilirubin at exchange value

In addition, study drugs will not be administered to any participant if the HIV NAT result comes back as positive at any time during the study.

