There will likely be no direct benefits from DTG for HIV-exposed neonates in Cohort 1A and 1B receiving one single dose of the study drug, in addition to the standard of care prophylaxis. Low risk HIV-exposed neonates in Cohort 2, receiving multi-dose of DTG in addition to ZDV, may potentially benefit from receiving a combination of DTG and ZDV to protect against vertical HIV transmission.

All participants will be carefully monitored for any possible side effects. In general, DTG is well-tolerated with a very good safety profile and paediatric adverse event data are similar to those observed in adults. The most common adverse reactions reported in adults from 3 clinical trials were insomnia, fatigue, and headache; occurring in less than 3% of participants. Hypersensitivity reactions have been reported in less than 1% of participants on DTG and study drug should be stopped immediately if suspected. Hepatotoxicity can rarely develop and monitoring for this condition is recommended (19). DTG has also been shown *in-vitro* to displace bilirubin from albumin in the presence of low albumin concentrations. The clinical relevance of this has not been established but in theory, displacement of bilirubin from albumin by DTG can lead to elevated free bilirubin which if untreated may lead to kernicterus. Because of this potential risk for bilirubin toxicity with high DTG concentrations, neonates known to be at risk for very high bilirubin levels will not be enrolled in this study, i.e., mother Rh-negative, etc. Bilirubin will also be performed at entry and during the study. To minimise any potential risk, we will first study a single dose of the DTG-DT in neonates older than 2 weeks of life, followed by a single dose in neonates less than 2 weeks of life. Only once safety

criteria are met in Stage 1 (Cohort 1A and Cohort 1B), will we proceed to enrol participants in Stage 2 (Cohort 2) where we will be administering multiple DTG doses.

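### Sections 10.6 and 13.6 stop dolutegravir on suspicion of hypersensitivity, while Section 10.8 continues it at Grades 1–2 and, pending confirmation, at Grade 3, without saying which instruction governs

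*Protocol*

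**What the plan says.** Protocol Section 10.6 (Hypersensitivity Reaction to Dolutegravir) gives two instructions. On suspicion: "Discontinue DTG as soon as a hypersensitivity reaction is suspected". On diagnosis: "if the diagnosis of DTG hypersensitivity is made DTG should never be re-started". Neither depends on severity grade. The section also states how cases are picked up: "The DAIDS Toxicity Table will capture symptoms and signs of possible DTG hypersensitivity, and if suspected, will be managed as a SAE". Section 13.6 repeats the first instruction: "study drug should be stopped immediately if suspected".

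Section 10.8 (Participant Study Drug Discontinuation Criteria) opens with its scope: "For all AEs/toxicity, the management and temporary/permanent discontinuation of the study drug should generally follow the criteria below". The same sentence adds that "clinicians should use their clinical judgment as to the best management for an individual participant". It then sorts events by grade:

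- Grades 1 and 2: "Continue the study drug. Manage using symptomatic measures and other concomitant medication, if appropriate".
- Grade 3: "Continue study drug pending receipt of the confirmatory laboratory tests/repeat observations", except where antiretrovirals must be substituted at once. Once the toxicity is confirmed and no other cause is found, treatment is held.
- Grade 4: withholding clinical cases while confirmation is awaited is left to the investigator's discretion. Drug is discontinued once the toxicity is confirmed without another cause.

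A separate list of permanent stops has two entries: any DAIDS Grade 4 event and bilirubin at exchange level. A stop for a positive HIV test follows. Hypersensitivity does not appear in 10.8, and 10.6 is not mentioned there.

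**The concern.** The section that a site would open to decide whether to keep dosing an infant differs from the two sections that deal with this reaction by name. The triggers differ in kind: 10.6 acts on suspicion, whereas 10.8 at Grade 3 acts after confirmation and exclusion of other causes, and at Grades 1 and 2 does not stop drug at all.

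Two things are at stake. The first is exposure in Cohort 2, where doses are repeated until day 28 of life and caregivers give them at home (Sections 8.4 and 9.2.3.1), so the site's stop instruction decides whether dosing continues. The second is consistent recording. The third Cohort 2 hold criterion in Section 11.1.3 is met by a related event that leads to permanent discontinuation. Sites that follow different sections could record the same reaction differently.

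**Working it through.** No figure in the plan rests on this point, so the check sets the passages side by side.

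**Step 1: instruction by grade for a suspected reaction.**

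| Situation | Sections 10.6 and 13.6 | Section 10.8 | Do they agree? |
|---|---|---|---|
| Grade 1–2 | Stop | Continue, treat symptoms | No |
| Grade 3, awaiting confirmation | Stop | Continue, with one exception | No |
| Grade 3, confirmed, no other cause | Already stopped; no re-start if diagnosed (10.6) | Hold, with laboratory values followed down to Grade 2 or below | No: a hold is not a permanent stop |
| Grade 4 | Stop; no re-start if diagnosed (10.6) | Withholding clinical cases before confirmation is discretionary; on the permanent-stop list | Largely in outcome, not in timing |

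**Step 2: does 10.8 defer to 10.6?** It restates two specific stops that are made elsewhere: the bilirubin stop (Section 10.4, where exchange transfusion ends treatment) and the HIV-test stop (Section 6.1). It does not restate the hypersensitivity stop and has no cross-reference. A reader can therefore take its list as complete.

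**Step 3: does 10.6 keep these cases out of the graded scheme?** It does not. It says the DAIDS table will capture the signs, and graded events are what 10.8 acts on. Managing a suspected case as serious brings expedited reporting and group review (Sections 10.3 and 14.2), but those sections do not say whether dosing continues.

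**Step 4: link to Section 11.1.3.** Take one related Grade 3 reaction that is not life-threatening.

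- First criterion (fatal or life-threatening, related): not met.
- Second criterion (25% with the same related Grade 3 or higher event): 3/12 = 25% or 6/24 = 25%, so one infant does not meet it.
- Third criterion (related event leading to permanent discontinuation): met if the stop is permanent, not met if it is a hold.

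Only the third criterion can apply. If the reaction is diagnosed as hypersensitivity, 10.6 makes the stop permanent, whereas the Grade 3 text of 10.8 calls it a hold.

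**Step 5: who is affected.** Stage 1 gives a single dose to 8 + 8 = 16 of the 40 infants, so no later dose remains to be stopped. The conflict concerns mainly the other 24.

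**The case against.** The strongest reply is that 10.8 is a general default and 10.6 a specific rule, and that specific rules ordinarily prevail. Section 10.8 says its criteria should *generally* be followed, allows clinical judgment, and has an exception at Grade 3. Section 10.6 is devoted to this reaction, 13.6 repeats the immediate stop, and Section 8.7 names a previous hypersensitivity reaction as a contraindication. A suspected case would also come before the SAE Evaluation Group.

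Much of this stands. A careful clinician could reach the 10.6 outcome without breaching 10.8. What remains is that permission to use judgment does not tell a site that another section requires a departure, and 10.8 names other specific stops while omitting this one.

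A reader might infer more than the text supports:

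- *That 10.8 orders a re-start after a Grade 3 hold.* It contains no re-start instruction, and 10.6 rules one out after diagnosis.
- *That 10.8 allows 72 hours of further dosing, which could be turned into a number of doses.* The 72 hours is a deadline for repeating laboratory tests where relevant, not a dosing allowance, and the intervals in Table 4 are only potential schedules.
- *That these reactions usually first appear at low grade.* Section 10.6 lists signs but gives no grades or frequencies.

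**Conclusion.** The sections contradict each other as written and must be reconciled. For a suspected reaction, the conflict is direct at Grades 1–2 and at Grade 3 before confirmation. At confirmed Grade 3 there is a mismatch between a hold and a permanent stop, and at Grade 4 a difference mainly of timing. The weight is moderate: 10.8 is softened by its own wording, the effect falls mainly on the 24 infants of Cohort 2, and Section 10.6 reports such reactions in under 1% of Phase 3 participants. The conclusion assumes that a suspected reaction can be graded below 4, but not that this is usual.

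A reader might also infer that any single stop for suspected hypersensitivity pauses Cohort 2, or that 10.8 disables the hold criterion. Neither follows. Section 11.1.3 needs the event to be related and the discontinuation permanent, and 10.6 makes it explicitly permanent only on diagnosis. Nor is 11.1.3 tied to the list in 10.8, so a related permanent stop made under 10.6 would still meet it. The supported point is narrower: whether a related Grade 3 reaction is recorded as a hold or as permanent can depend on which section the site follows.

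No view is taken here on which clinical rule is right.

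**What to change.** Reconcile Sections 10.6, 10.8 and 13.6 so that they state one rule for suspected and one for diagnosed hypersensitivity, and add a cross-reference in 10.8 saying how the graded criteria relate to that rule. State whether a stop made under it counts as a hold or as a permanent discontinuation for Section 11.1.3, including when the suspicion is later ruled out. The sponsor decides the clinical content.

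The cost is about one sentence and a cross-reference in 10.8, with matching words elsewhere where needed, and submission for approval as a protocol modification under Section 13.4. Sample size, visits and analyses do not change. It is best done before Cohort 2 dosing starts.

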## 10.7. Risk of Elevated Bilirubin Levels in neonates

### 10.7.1. Bilirubin Metabolism in Neonates

Between 25-50% of all term neonates develop clinical jaundice characterized by high levels of unconjugated/free bilirubin. The serum bilirubin of term neonates rises to a peak of 103 to 137  $\mu\text{mol/L}$  by 3 days of life and then falls. A rise to 205  $\mu\text{mol/L}$  is still within the normal physiological range and may be attributed to an increase in bilirubin production, reduced uptake of bilirubin from plasma, reduced conjugation (immature UGT1A1 enzyme activity) and decreased hepatic excretion of bilirubin (46). Bilirubin values exceeding 342  $\mu\text{mol/L}$  have been considered levels at which kernicterus can occur (48, 49). Phototherapy are the mainstay of treatment for unconjugated hyperbilirubinemia resulting in less free bilirubin available to cross the blood-brain barrier, and thereby protecting against kernicterus and associated brain damage. In rare cases, exchange transfusions are performed to rapidly decrease bilirubin values.

Normally, newborn produce more bilirubin compared to adults. After birth, fetal haemoglobin is broken down and replaced with adult haemoglobin. Heme-containing proteins from old red cells are converted to insoluble bilirubin which is then bound to albumin and transported to the liver. Once in the liver, the enzyme UGT1A1 converts the unconjugated bilirubin to water-soluble conjugated bilirubin. End-products of this process, i.e., bile, is then secreted into the digested tract with bilirubin metabolites leaving the body through faeces (50).

The bilirubin-conjugating capacity of infants is dependent on UGT1A1 enzyme activity, which is typically slow at birth but rapidly increases in the first months of life. UGT1A1 is expressed at 1% of adult levels between 30- and 40-weeks' gestation, reaching adult levels by 14 weeks of postnatal life (51). Immature UGT1A1 early in life may lead to less conjugation and contribute to elevated free bilirubin levels leading to the jaundice in the newborn.

